Evaluating the Efficacy and Compatibility of Efinaconazole 10%
Solution (Jublia) for the Treatment of Toenail Onychomycosis in
Patients Wearing Toenail Polish Compared to Those without
Polish

Study Protocol & Statistical Analysis Plan

NCT03110029

January 14, 2019

[name]., Principal Investigator
University of Alabama at Birmingham
Birmingham, AL 35294

Evaluating the efficacy and compatibility of efinaconazole 10% solution (Jublia) for the treatment of toenail onychomycosis in patients wearing toenail polish compared to those without polish

Primary investigator: [name]

Research question

Topical efinaconazole 10% solution is known to be an efficacious and safe treatment modality for toenail onychomycosis. We propose to examine the compatibility of topical efinaconazole and nail polish in patients with distal and lateral subungual onychomycosis (DLSO). We posit that treatment of DLSO with efinaconazole 10% solution will not be adversely affected by the application of nail polish. We will have an interim compatibility analysis at 12 weeks and a final analysis at 52 weeks. We will also look at the efficacy of treating DLSO in patients wearing toe nail polish as compared to no polish when topical efinaconazole 10% (Jublia) solution is applied in the subungual space.

Background

DLSO is a commonly encountered dermatological disease. DLSO, which is caused by a variety of dermatophyte organisms, typically has an indolent and chronic course. Untreated, onychomycosis can pose a potential risk of spreading fungal infection to distant sites, which is especially true for elderly patients with comorbid diseases such as diabetes mellitus, peripheral vascular disease, or immunosuppression. Traditional therapies for DLSO have been comprised of mainly oral antifungal medications; however many of these treatments have side effect profiles that limit their applicability in this elderly population. Because of the potential toxicities associated with traditional oral therapies for DLSO, there has been great interest in finding safe and efficacious alternatives.

Topical efinaconazole 10% solution (Jublia), which is a new FDA approved treatment for DLSO, has been shown to be efficacious and well tolerated by patients (Elewski, *et al*). In clinical trials, efinaconazole was applied daily to the nail plate, lateral and proximal nail folds, hyponychium and undersurface of the nail. Systemic absorption and associated toxicities are minimized with this topically applied medication. Complete cure and mycologic cure rates using efinaconazole 10% solution were within the range of those seen with oral antimycotic medications (Sporanox and Lamisil package inserts). Because efinaconazole 10% solution was applied in clinical trials directly onto clean, dry toenails that were free of toenail polish, it is not currently known if efficacy may be influenced by the wearing of toenail polish or if toenail polish is adversely modified by application of this medication. Toenail polish is very popular among women, especially during summer months, and wearing toenail polish is currently a major limitation of topical efinaconazole for treatment of DLSO. From our personal experience with efinaconazole solution, our patients have commented their nail polish becomes slightly tacky with daily application to the nail plate, but that application is still possible without discontinuing polish or treatment.

The dermatophytes causing DLSO primarily reside in the nail bed and subungual space, especially early in the disease process. Therefore we posit that application of efinaconazole solution to the nail bed and subungual space (subungual delivery) should be as efficacious as application to the nail plate. In fact, subungual delivery may prove to be more efficacious, as that space harbors the dermatophytes of DLSO.

Methods

We will enroll 20 female subjects who fulfill the inclusion and exclusion criteria for a 52 week study (48 weeks treatment, 4 weeks post treatment follow-up). Ten women who self identify as frequently wearing toenail polish will be placed into the study group, while the control group will be comprised of 10 women who agree to abstain from wearing toenail polish during the length of the study. To avoid having a significant gender difference between both groups, male patients will be excluded since they would likely be exclusively placed into the control group. Because nail size is proportional to body size, with men having larger nails on average, excluding men will prevent introduction of bias in this study. Patients with symptomatic tinea pedis at screening will be treated with Luzu for 2 weeks.

Treatment methods will be similar to those described by Elewski, *et al.* Briefly, all patients will self-apply 1 drop of efinaconazole 10% solution to the hyponychium and undersurface of the nail every night before bed. Patients in the study group will not be restricted with respect to the brand of nail polish, however gel and plastic based polishes that are used in salons and that require curing will be prohibited. Patients in the study group will also be permitted to touch up their polish if needed in the morning without constraint.

Patients will be seen in clinic for this study at screening and then again at baseline. After baseline, patients will be clinically evaluated every month for the first 3 months, followed by 8-week intervals, with the final visit at week 52. Our primary outcome, compatibility of topical efinaconazole solution with wearing polish, will be assessed at every visit.

An interim analysis of our primary outcome will be performed at 3 months and these results will be presented in poster and oral format as well as submitted in manuscript form for publication in a peer reviewed journal. We hope to present these data as oral and poster presentations at the summer AAD, the Fall Clinical Dermatology Conference or other similar national meeting. We will also submit a manuscript regarding the compatibility of treatment with nail polish for publication in an appropriate dermatology journal for US audiences. At the conclusion of this study we will present our findings in poster and oral format, as well as submit a manuscript for publication in the Journal of The American Academy of Dermatology.

Subjective effect of the medication on polish will be assessed with the following series of questions to which patients can answer yes or no:

- Were you able to apply the medication under your nail?
- Are you overall satisfied with Jublia?
- Is your polish tacky in the morning?

Patients will also answer the following question, which will be answered using a Likert or VAS scale where 0 represents no alteration in polish and 10 represents complete destruction of the polish:

- Is the quality of your polish diminished with use of Jublia?

We anticipate that some patients may note diminished quality of polish with use of Jublia on a daily bases, however we anticipate that this effect will be minimal.

Secondary outcomes will include efficacy and safety. Using 3rd party blinding, DLSO will be assessed at baseline and at every subsequent visit using the onychomycosis severity index, measuring percent of the target nail involved, and grading the infection from mild to moderate to severe. The target nail will be notched at baseline, thereby allowing overall nail growth to be assessed at each visit and disease free nail growth to be measured every 8 weeks. Photos of the nails will be taken every 8 weeks, including close up photos of the target nail with and without an outline of the onychomycosis. Fungal testing will be done at screening, 3 months, 7 months, end of treatment (48 weeks), and end of study (52 weeks). Clinical and mycologic cure will be evaluated at week 52. Mycology cultures will be processed at the fungal lab of the University of Texas, with whom the UAB Dermatology Research unit has a contract. The following will comprise our inclusion and exclusion criteria:

Inclusion:

- Female age 18-75,
- Clinical diagnosis of DLSO affecting at least 1 great toenail diagnosed with positive potassium hydroxide microscopy. A culture for a dermatophyte will be collected but positive culture is not necessary for inclusion in the study. Cultures for patients with a previous positive culture can be waived at the discretion of the investigator.
- Suitable for application of topical antifungal therapy, in the opinion of the investigator
- Target toenail thickness of 3mm or less as measured by digital caliper, as thickness greater than 3mm may allow inclusion of patients with severe onychomycosis, and this was the criteria used in the pivotal trial using topical efinaconazole for onychomycosis (Elewski BE, et al.)
- Women of childbearing potential will be required to use birth control and a negative urine pregnancy test must be documented prior to initiating treatment

Exclusion

- History of immunosuppression or concurrent use of immunosuppressant drugs
- History of uncontrolled diabetes mellitus
- History of psoriasis or any other condition that might interfere with the toenail evaluation
- Three or more dermatophytomas (streaks) on the target nail
- Severe DLSO of the target nail
- Patients who cannot refrain from wearing gel or plastic based polishes that are used in salons and that require curing

Conclusion

Treatment options for DLSO has until recently been comprised primarily of oral medications that were associated with significant possible toxicities. New research has revealed topical efinaconazole 10% solution (Jublia) to be a promising alternative treatment for DLSO, however it is unknown if this treatment is both compatible and efficacious in persons wearing toenail polish. Our proposal aims to examine the compatibility and efficacy of wearing polish while using efinaconazole 10% solution for DLSO.

Citations

Elewski BE, *et al.* Efinaconazole 10% solution in the treatment of toenail onychomycosis: Two phase III multicenter, randomized, double-blind studies. *J Am Acad Dermatol.* 2013 Apr;68(4):600-8.

Sporanox (itraconazole) [package insert]. Titusville, NJ: Janssen Pharmaceuticals Inc; 2012.

Lamisil (terbenafine HCl) [package insert]. East Hanover, NJ: Novartis Pharmaceuticals Corp; 2012.

Evaluating the Efficacy and Compatibility of Eflaconazole 10% Solution (Jublia) for the Treatment of Toenail Onychomycosis in Patients Wearing Toenail Polish Compared to Those Without Polish

NCT03110029

Statistical analysis consisted of 2-tailed T-tests to study associations between continuous variables. P-values less than 0.05 were considered statistically significant.

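### The plan posits that polish does no harm to treatment, but its only analysis rule can detect a difference, cannot support absence of harm, and does not fit week-52 cure

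*Combined protocol and SAP*

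**What the plan says.** The Research question sets out the hypothesis: "We posit that treatment of DLSO with efinaconazole 10% solution will not be adversely affected by the application of nail polish". It then adds a between-group aim: "We will also look at the efficacy of treating DLSO in patients wearing toe nail polish as compared to no polish". Background explains why the question is open: "it is not currently known if efficacy may be influenced by the wearing of toenail polish". The Conclusion returns to it: "Our proposal aims to examine the compatibility and efficacy of wearing polish while using efinaconazole 10% solution for DLSO".

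Methods names compatibility with polish as the primary outcome and places efficacy below it: "Secondary outcomes will include efficacy and safety". The groups are 10 and 10, formed by the women's own habits rather than by randomisation: "Ten women who self identify as frequently wearing toenail polish will be placed into the study group", against 10 who agree to abstain. For efficacy, "DLSO will be assessed at baseline and at every subsequent visit using the onychomycosis severity index", together with the percentage of the target nail involved and a mild, moderate or severe grade. In addition, "Clinical and mycologic cure will be evaluated at week 52".

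The statistical plan is two sentences after the citations. They specify two-tailed t-tests for continuous variables and a significance level of 0.05. The document gives no margin, confidence interval, power statement or method for a yes/no outcome.

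**The concern.** The hypothesis concerns the absence of an adverse effect. A t-test of no difference addresses the opposite question. A significant result would be evidence that the groups differ, but a non-significant one says only that a difference was not shown. Supporting the hypothesis would need an interval read against a margin, and the plan has neither. Cure, read in the ordinary way as achieved or not achieved, is also outside a rule written for continuous variables.

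At stake is what the trial may conclude about efficacy. With 10 women per group a non-significant result is likely even if polish does appreciable harm. Without an interval, a reader cannot tell no important loss of efficacy from too few women to know. Methods commits to publishing the findings, and Background describes polish wearing as a major limitation of this treatment, so the distinction matters to readers.

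**Working it through.** **Inputs from the document.** 10 women per group (Methods); two-sided 0.05 and t-tests (statistical statement); continuous efficacy measures and week-52 cure (Methods). **Assumed, because the document gives none:** true effects in SD units, the baseline to week-52 correlation, retention and cure counts.

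**The plan's own figure.** The total of 20 cannot be reproduced, since no effect size, SD, power or cure rate accompanies it. Working backwards, 10 per group gives 80% power in a two-sided t-test only for a true difference of about 1.32 SD (noncentral t, 18 degrees of freedom).

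**Precision, unadjusted.** The 95% half-width in SD units is t(0.975, 2n−2) × √(2/n).
- n = 10: 2.101 × √0.2 = 2.101 × 0.447 = 0.94 SD.
- n = 8 (assumed retention): 2.145 × √0.25 = 2.145 × 0.5 = 1.07 SD.

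An observed difference of exactly zero would therefore leave harm of up to 0.94 SD not excluded with all 20 women.

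**Precision, adjusted for baseline.** The residual SD is multiplied by √(1−r²) and one degree of freedom is lost, so the half-width is about t(0.975, 17) × √(2/10) × √(1−r²). This ignores the small extra variance from any baseline imbalance.
- r = 0.5: 2.110 × 0.447 × 0.866 = 0.82 SD.
- r = 0.7: 2.110 × 0.447 × 0.714 = 0.67 SD.

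**Chance of p ≥ 0.05 despite real harm** (unadjusted test, noncentral t with noncentrality d/√(2/n)):

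| True harm (assumed) | 10 per group | 8 per group (assumed) |
|---|---|---|
| 0.5 SD | 1 − 0.185 = 81% | 1 − 0.154 = 85% |
| 0.8 SD | 1 − 0.395 = 60% | 1 − 0.320 = 68% |
| 1.0 SD | 1 − 0.562 = 44% | 1 − 0.461 = 54% |
| Harm at which the chance is 50% | 0.93 SD | 1.05 SD |

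**Cure at week 52.** For equal counts, the Newcombe 95% half-width is √[(p−l)² + (u−p)²], where l and u are the Wilson limits for one group. For 2/10 in each group, l = 0.057 and u = 0.510, so the half-width is √(0.143² + 0.310²) = 0.341. Across assumed equal counts:
- 10 per group: ±27.8 points at 0/10, ±34.1 at 2/10, ±37.3 at 5/10.
- 8 per group: ±32.4 points at 0/8 to ±40.3 at 4/8.

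If Fisher's exact test were used and one group had no cures, 4/10 in the other would give p = 0.087; it takes 5/10 (p = 0.033) to fall below 0.05.

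**The case against.** The strongest reply is that the document never commits the error. A reader might infer that p ≥ 0.05 will be reported as showing that polish does no harm. The document does not say so: it posits the hypothesis and plans to look at efficacy, and it is silent on how a non-significant result will be read. A reader might also infer that the t-test is the designated polish versus no-polish efficacy test. That too is unstated, since no groups, variables or time points are named and the rule could be meant for the polish-quality score or for change within a group. Cure is to be evaluated, which could mean described only. All of this stands. What remains is that no other rule is available for this comparison, and the one given cannot support the hypothesis.

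Second, this is a 20-woman study with efficacy secondary, and the hypothesis sentence sits among statements about compatibility. It would be wrong to extend the point to the primary outcome. But the sentence speaks of the treatment of DLSO, and efficacy with polish is named in the title, the Research question, Background and the Conclusion.

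Third, the 0.94 SD figure assumes an unadjusted week-52 comparison, while baseline values are collected. This stands: adjustment could narrow the interval, hence the 0.82 and 0.67 SD figures. Even the narrowest of these leaves sizeable harm not excluded.

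Fourth, self-selection is a separate design limit that no interval or margin removes. It does not strengthen this point, but it does limit what any result can be taken to show.

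**Conclusion.** The point holds as a gap between hypothesis and analysis for the secondary efficacy comparison: nothing specified can support absence of harm, and nothing specified fits week-52 cure. With 10 per group, a zero difference in a continuous measure leaves harm of up to 0.94 SD not excluded without adjustment, or about 0.82 or 0.67 SD with adjustment at an assumed correlation of 0.5 or 0.7. Equal assumed cure counts leave about ±28 to ±37 points. In the unadjusted test, a non-significant result is more likely than not whenever true harm is below about 0.93 SD. The half-widths in SD units need only the group size and the level, plus the assumed correlation for the adjusted figures. The non-significance rates and cure intervals also need the assumed effects and counts. The document does not support saying that the investigators will misread a null result, or that the primary outcome is affected. It should be fixed, because the change governs what the trial may say about efficacy and needs no new data collection.

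**What to change.** Change the SAP wording and the report as follows.

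1. Report the week-52 polish-minus-no-polish difference in percent of target nail involved and in the onychomycosis severity index, each adjusted for its baseline value by ANCOVA, with a 95% confidence interval. Methods already collects both at baseline.
2. Report risk differences for clinical cure and for mycologic cure with Newcombe or exact 95% intervals.
3. State that p ≥ 0.05 is not evidence of no adverse effect. Give the harmful-side limit (upper for nail involvement and severity index, lower for cure) as the largest loss of efficacy the data do not exclude. Do not describe efficacy as not adversely affected unless a margin was fixed before outcomes were seen. Otherwise label the comparison as estimation only and set no margin afterwards; the statistical statement is in the past tense, so this may already apply.
4. Note that the groups are self-selected, so neither a difference nor its absence can be attributed to polish alone. Baseline adjustment does not remove this.

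The cost is wording and analysis time, plus one degree of freedom for the covariate; no patients, visits or procedures are added. The efficacy statement will be less favourable and probably inconclusive. Adjustment may narrow the intervals somewhat, but 10 per group remains the limit on precision.

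### The groups are self-selected and the only stated test is an unadjusted t-test, so a baseline severity gap can bias the secondary polish versus no-polish efficacy comparison

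*Combined protocol and SAP*

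**What the plan says.** Under Methods, group membership follows from the women themselves. For the polish group: "Ten women who self identify as frequently wearing toenail polish will be placed into the study group". The comparison group is likewise defined by willingness: "the control group will be comprised of 10 women who agree to abstain from wearing toenail polish during the length of the study". No randomisation, matching or stratification is described.

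The Research question section expects no harm from polish: "We posit that treatment of DLSO with efinaconazole 10% solution will not be adversely affected by the application of nail polish". It also announces an efficacy comparison between women with and without polish. Methods ranks this below compatibility: "Secondary outcomes will include efficacy and safety".

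Severity is recorded from the start: "DLSO will be assessed at baseline and at every subsequent visit using the onychomycosis severity index", together with percent of the target nail involved. At the end, "Clinical and mycologic cure will be evaluated at week 52".

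The analysis text at the end of the document is two sentences. One sets significance at P < 0.05; the other reads "Statistical analysis consisted of 2-tailed T-tests to study associations between continuous variables". It names no outcome, time point, covariate or scale (final value or change).

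On balance between groups, the design acts on sex: "To avoid having a significant gender difference between both groups, male patients will be excluded". For severity there are only eligibility limits: target nail thickness of 3 mm or less, fewer than three dermatophytomas, and no severe disease of the target nail.

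**The concern.** Women who habitually wear polish and women content to go without it for a year may differ in how bad their nails are at entry. The eligibility limits narrow any such difference but do not balance mild and moderate disease between the groups. The plan accepts, in excluding men, that group make-up can bias this comparison. It gives the starting value of the outcome itself no role in the analysis, although that value is collected.

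Direction matters because the hypothesis is one of no harm. If the polish group starts milder, an unadjusted comparison can hide a real harm and so favour the expected conclusion. If it starts worse, the comparison can create a false harm. Week-52 clinical and mycologic cure compare the same two groups and can be confounded in the same way.

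The concern is a systematic gap due to self-selection. Chance imbalance does not raise the overall error rate; it distorts the particular trial in which it occurs and costs precision.

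**Working it through.** **Inputs from the documents:** 10 women per group, two-sided t-test, alpha 0.05. No effect size, SD, power or dropout is given, so the sample size of 20 cannot be reproduced.

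**Assumed inputs:** baseline gap g = 0.5 SD (also 0.25 SD); correlation between baseline and week-52 severity r = 0.3 to 0.7; normal data with unit SD.

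**Precision.** The standard error of a difference in means is √(2/10) = 0.447 SD. Exact t-test power (18 df) is 56% for 1 SD and 19% for 0.5 SD.

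**Bias formulas.** Let f be the week-52 gap that would exist with no polish effect. A positive sign means the polish group is worse.

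- Final-value t-test: bias = f
- Change-from-baseline t-test: bias = f − g
- ANCOVA on baseline: bias = f − r·g

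The documents do not say how a gap would evolve, so three cases are taken: (1) regression to a common mean, f = r·g; (2) a stable group difference, f = g; (3) the gap closes by week 52, f = 0.

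**No polish effect, g = 0.5.** Each cell gives bias in SD, then the false-positive rate, as r goes from 0.3 to 0.7 (40,000 simulated trials per setting).

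| Case | Final value | Change | ANCOVA |
|---|---|---|---|
| 1 | 0.15 to 0.35; 6–11% | −0.35 to −0.15; 10–7% | 0; 5% |
| 2 | 0.50; 18–19% | 0; 5% | 0.35 to 0.15; 11–7% |
| 3 | 0; 5% | −0.50; 14–28% | −0.15 to −0.35; 6–17% |

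Example, case 1 with r = 0.5: final value 0.5 × 0.5 = 0.25 SD; change 0.25 − 0.50 = −0.25 SD; ANCOVA 0.25 − 0.25 = 0. The exact noncentral t for the final value in case 1 gives 6.2%, 8.3% and 11.5% at r = 0.3, 0.5 and 0.7, in line with the simulation.

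**Worst case.** If f lies anywhere between 0 and g, the largest absolute bias is g = 0.50 SD for either t-test. For ANCOVA it is max(r, 1 − r)·g, which is 0.5 × 0.5 = 0.25 SD at r = 0.5 and 0.7 × 0.5 = 0.35 SD at r = 0.3 or 0.7.

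**Masked harm.** True harm 1 SD, polish group 0.5 SD milder at baseline. Each cell gives the estimate in SD, then power.

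| Case | Final value | Change | ANCOVA |
|---|---|---|---|
| 1 | 0.85 to 0.65; 43–28% | 1.35 to 1.15; 67–88% | 1.00; 55–79% |
| 2 | 0.50; 18–19% | 1.00; 43–78% | 0.65 to 0.85; 27–66% |
| 3 | 1.00; 56% | 1.50; 76–98% | 1.15 to 1.35; 67–96% |

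With no gap, power is 56% (final value), 43–78% (change) and 57–82% (ANCOVA). Where an estimate exceeds 1.00, the extra power comes from overstating the harm and is no gain.

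**Smaller or no gap.** At g = 0.25 the final-value false-positive rate is 5–7%, 8% and 5% in cases 1, 2 and 3. With no systematic gap, all three analyses stay at 5%.

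**Floor effect.** Percent of nail involved cannot go below zero. If 31% or 50% of control values sit at the floor at week 52 (g = 0.5), the change score in case 2 is no longer unbiased (−0.11 or −0.20 SD). In case 1 its bias is −0.24 to −0.42 SD, while ANCOVA stays at 0.

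**Cure.** Assume cure of 20–50% and odds of cure 1.5 to 3 times higher per SD milder, averaged over the spread of severity. A group 0.5 SD milder then has cure of 23–28% against 20%, 34–40% against 30%, or 55–61% against 50%. The shift is about 3 to 11 percentage points.

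**The case against.** The statistical sentence does not say that its t-tests are between groups or on severity; paired tests within a group would also fit the words. That is true, but on that reading the announced polish versus no-polish comparison has no test at all, so the plan is no better off.

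Nothing in the documents suggests that the groups differ in severity, and the entry criteria limit how far they could. This stands. At a 0.25 SD gap the effect on error rates is small, and the 18–19% figure needs both a 0.5 SD gap and a fully stable difference. The case 1 bias of 0.15 to 0.35 SD is also below one standard error (0.447 SD). With 10 per group the comparison could not establish absence of harm even if perfectly balanced.

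ANCOVA is not always the better analysis. This also stands: if the gap closes by week 52, it is more biased than the final-value t-test, and if the difference is stable, the change score is unbiased where ANCOVA is not. The argument for leading with ANCOVA is its smaller worst-case bias and its precision at moderate or high r. The remaining uncertainty is the reason for a sensitivity analysis.

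Two compatibility items, being able to apply the drug under the nail and overall satisfaction, could be asked of both groups, and satisfaction might depend on severity. The plan, however, defines its primary outcome as compatibility with wearing polish, so confining the point to the secondary comparison is fair.

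**Conclusion.** The concern holds, as an inexpensive improvement to a secondary analysis. The groups are self-selected, baseline severity is collected, and the stated test makes no use of it. How much this matters depends on a gap the documents neither report nor rule out. Under the assumed 0.5 SD gap and r = 0.3 to 0.7, the final-value t-test is biased by 0 to 0.50 SD, with 5% to 19% false positives. A change-score t-test is biased by 0 to 0.50 SD the other way, with 5% to 28%. ANCOVA is biased by at most 0.25 to 0.35 SD, with 5% to 17%. No method is best in all three cases. No adjustment removes confounding by unmeasured differences between polish wearers and abstainers.

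**What to change.** For the severity index and percent of target nail involved:

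- Analyse the week-52 value by ANCOVA with group and the baseline value of the same measure, and report the adjusted difference with a 95% CI.
- As a sensitivity analysis, report the between-group difference in change from baseline with a 95% CI.
- State the assumption behind each: regression to a common mean for ANCOVA, a stable group difference for change. If the two disagree, say that the conclusion depends on which assumption is believed.
- Tabulate baseline severity by group.
- Describe the comparison as non-randomised and exploratory, and note that week-52 clinical and mycologic cure may be confounded by the same baseline difference.

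The cost is SAP wording, one table and one degree of freedom; no new data are needed. ANCOVA gains little or no precision if r is about 0.3 or less (power for 1 SD of 57–58% against 56%). The statistical paragraph is written in the past tense, so if these analyses are added after the results are known, they must be labelled post hoc.

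### The tackiness question, part of the primary compatibility outcome, is recorded only as yes or no, so it cannot tell slight tackiness from severe tackiness

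*Combined protocol and SAP*

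**What the plan says.** The Methods section names the outcome: "Our primary outcome, compatibility of topical efinaconazole solution with wearing polish, will be assessed at every visit". It introduces three questions with the words "Subjective effect of the medication on polish will be assessed with the following series of questions to which patients can answer yes or no". They cover whether the woman could get the medication under the nail, whether she is satisfied overall, and "Is your polish tacky in the morning". A fourth question, on loss of polish quality, uses a "Likert or VAS scale where 0 represents no alteration in polish and 10 represents complete destruction of the polish". The investigators expect some women to notice a loss of quality, "however we anticipate that this effect will be minimal".

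The Background section reports from practice that "our patients have commented their nail polish becomes slightly tacky with daily application to the nail plate", and adds that those patients could carry on with both polish and treatment. In this trial the drop goes under the nail rather than on the plate.

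The statistical statement that closes the document gives one method: "Statistical analysis consisted of 2-tailed T-tests to study associations between continuous variables", with significance at P below 0.05. It names no analysis for yes/no answers, no rule for combining the four items, no threshold for compatibility and no sample-size calculation. The trial enrols 20 women: ten who wear polish and ten who abstain.

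**The concern.** Tackiness is a matter of degree, and the Background treats a slight degree as tolerable. The question as asked has one category for everything above none, or above whatever each woman privately counts as tacky. A high proportion answering yes could therefore mean a trivial nuisance in most women or unwearable polish in most women. A change in tackiness between visits shows only if a woman crosses her own line.

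The 3-month compatibility results are intended for presentation and publication, so a tackiness percentage with no degree attached may be among the first results reported. The detail is lost when the form is filled in, and no later analysis can restore it. The plan gives no reason for the yes/no format, and the next question on the same form already uses a 0-10 scale.

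**Working it through.** The plan states no effect size, SD, expected response rate or power, so there is no figure of its own to reproduce. The checks below use the plan's ten polish wearers. All other inputs are assumptions and are marked as such.

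**1. What the form can record.** Take one woman with slightly tacky polish and one with severely tacky polish.

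| Item | Slight | Severe |
|---|---|---|
| Tacky in the morning (yes/no) | yes | yes |
| Polish quality (0-10) | graded damage | graded damage, probably higher |
| Degree of tackiness | not recorded | not recorded |

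The quality score will often separate the two women. It does not say how tacky the polish was, since damage may also reflect other changes.

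**2. How little the yes-rate can move.** Assume true tackiness on a 0-10 scale is normal with SD 1.5, and that anything above 0.5 is answered yes.
- Mean 2: Φ((2 − 0.5)/1.5) = Φ(1.00) = 84% yes.
- Mean 7: Φ((7 − 0.5)/1.5) = Φ(4.33) ≈ 100% yes.

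A 5-point difference in mean tackiness moves the expected count only from about 8.4 to about 10 of ten women. If women use a stricter personal threshold, the figures change. The plan does not define the threshold.

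**3. Information kept by a yes/no item.** For a normal underlying scale cut so that a proportion p falls on one side, the efficiency relative to the graded score is φ(z_p)² / [p(1 − p)].

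| Split | Calculation | Kept | Lost | Ten women count as |
|---|---|---|---|---|
| 50/50 | 0.3989² / 0.25 | 64% | 36% | 6.4 |
| 30/70 | 0.3477² / 0.21 | 58% | 42% | 5.8 |
| 20/80 | 0.2800² / 0.16 | 49% | 51% | 4.9 |
| 10/90 | 0.1755² / 0.09 | 34% | 66% | 3.4 |

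The loss passes one half only at about 20/80 or more uneven. The 84% in step 2 would be such a split.

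**4. Precision in one group of ten.** With 3 of 10 answering yes, the exact 95% interval is 7% to 65%. With 5 of 10 it is 19% to 81%. For a graded mean, the half-width is t(0.975, 9)/√10 = 2.262/3.162 = 0.715 SD. That is 0.715 × 1.5 = 1.07 points if the SD is 1.5, and 0.715 × 2 = 1.43 points if the SD is 2 (both SDs assumed). The two scales are not directly comparable, but only the second interval says how tacky the polish was.

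**The case against.** The strongest reply is that the primary question set already has a graded item. A reader might infer that slightly tacky polish and ruined polish score the same on the primary outcome. They do not: the fourth question runs to 10 for total loss of the polish, and the stated expectation of a minimal effect refers to that question. This stands, and it confines the point to the tackiness item.

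A reader might also infer that the protocol predicts slight tackiness in this trial. The Background remark concerns application to the nail plate, so it shows what the investigators regard as tolerable, not what they expect under the nail. If delivery under the nail causes less tackiness, a graded answer is better able to show it.

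A third tempting inference is that most of the power of a 10 versus 10 comparison is lost. For an assumed difference of 1.3 SD, power is 78% with a graded score and 30-39% with yes/no answers and Fisher's exact test; at 1.0 SD it is 56% against 14-22%. But the plan does not name Fisher's test, which is conservative at this size. The t-test applied to 0/1 data, itself approximate here, gives 48-58% and 27-39%. More fundamentally, tackiness has no between-group contrast, because controls wear no polish. For the other two yes/no items, the documents never say that controls answer them or that the groups are compared on them.

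Finally, not every yes/no item is a fault. Being able to apply the medication is naturally a feasibility question, and a yes/no satisfaction item is defensible in a small descriptive study.

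**Conclusion.** The point holds for one item. Tackiness is part of the primary outcome, its degree is lost at collection, and the quality score does not supply it. Under an assumed normal underlying scale the cost is about 36-42% of the information for splits from 50/50 to 30/70, and 51-66% for splits from 20/80 to 10/90. This is a loss of description and precision in ten women. The documents support no between-group power claim for tackiness.

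This is a modest, inexpensive improvement and does not invalidate the trial. It also leaves open a wider gap: the plan does not say which of the four items, at which visit and against what threshold, defines compatibility.

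**What to change.** In the question list in Methods, replace the yes/no tackiness item with: *How tacky is your polish in the morning?* scored 0-10 (0 = not at all, 10 = completely tacky). In the statistical section, state that for the ten polish wearers the mean with its 95% confidence interval will be reported, together with the within-woman change across visits. Keep a yes/no version (0 versus 1 or more) as a descriptive summary. A score of this kind suits the t-tests on continuous variables that the plan already names. Overall satisfaction may be graded the same way if wished; the question on being able to apply can stay yes/no.

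The cost is one changed response format, with no added patients, visits or staff. The downside is that yes/no answers already collected cannot be compared directly with the scores, because each woman set her own threshold. Keep those answers, report them separately, and use the graded item from the change onward.
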